7.2.3 Efficacy of the Treatment of Breakthrough BEs

At the end of a BE, treatment efficacy will be assessed by the patient (together with the investigator in case of on-site treatment) using the predefined criteria detailed in **Table 2**.

Table 2 Efficacy Assessment of the Treatment of Breakthrough BEs

Excellent	Bleeding was completely stopped within 3 days in case of minor bleeds, within 7 days in case of major bleeds, and within 10 days in case of gastrointestinal bleeds
Good	Bleeding was completely stopped, but time and/or dose slightly exceeded expectations
Moderate	Bleeding could be stopped only by significantly exceeding time and/or dose expectations
None	Bleeding could be stopped only by using other VWF-containing products

The **proportion of BEs successfully treated with IMP** will be evaluated for all BEs taken together and by BE severity. All efficacy ratings assessed as either 'excellent' or 'good' will be considered 'successfully treated.'

7.2.4 Surgical Prophylaxis Data

The following surgery-related parameters will be documented:

- Type of surgery (planned or emergency)
- Location of surgery
- Severity of surgery (minor, major) (see definitions under **(a)** below)
- Expected and actual duration of surgery
- Expected average/maximum and actual blood loss
- Pre-, intra-, and postoperative IMP administration data (see definitions under **(b)** below)
- Pre-, intra-, and postoperative FVIII and VWF:Ac plasma levels (see definitions under **(b)** below)
- Routine safety laboratory
- Presence of wound haematomas
- Vital signs
- Details on concomitantly administered products
- Blood transfusion requirements
- Brief narrative describing the outcome of the intervention
- Efficacy assessment at the end of surgery by surgeon (see **Section 7.2.5.1**)
- Efficacy assessment at the end of the postoperative period by haematologist (see **Section 7.2.5.2**)
- Overall efficacy assessment at the end of the postoperative period by the investigator (see **Section 7.2.5.3**)
- Monitoring of AEs

For details regarding the time points of data collection, refer to the flow chart of assessments for surgical prophylaxis on **page 27**.

(a) Severity of surgery

Surgeries are defined as **major** if any of the following criteria are met:

- General or spinal anaesthesia required
- Opening into the great body cavities required
- Severe haemorrhage during surgery possible
- Haemostatic therapy for at least 6 days required
- Orthopaedic interventions involving joints (ankle, knee, hip, wrist, elbow, shoulder)
- 3rd molar extraction or extraction of ≥ 3 teeth
- Surgeries/conditions in which the patient's life is at stake

The classification is made prospectively. All other surgeries are classified as **minor**.

(b) Definitions of periods and time points before, during, and after surgery

- **Preoperative** is defined as the time period of up to 3 hours before the start of surgery.
- The **end of surgery** is defined as the time immediately after the last surgical suture.
- **Postoperative** is the period from the end of surgery to the time the patient returns to his or her regular VWF treatment regimen.
- The **end of the postoperative period** is the time the patient returns to his or her regular VWF treatment regimen.

7.2.5 Efficacy in Surgical Prophylaxis

Efficacy will be assessed at the end of surgery by the surgeon (see **Section 7.2.5.1**) and at the end of the postoperative period by the haematologist (see **Section 7.2.5.2**). In both cases, pre-defined assessment criteria will be used. In addition, an overall assessment of efficacy will be made at the end of the postoperative period by the investigator (see **Section 7.2.5.3**).

7.2.5.1 At the End of Surgery (by Surgeon)

At the end of surgery, the haemostatic efficacy of *Wilate* will be assessed by the surgeon using the criteria listed in **Table 3**.

Table 3 Efficacy Assessment at the End of Surgery

Excellent	Intraoperative blood loss was lower than or equal to the average expected blood loss for the type of procedure performed in a patient with normal haemostasis and of the same sex, age, and stature
Good	Intraoperative blood loss was higher than the average expected blood loss but lower or equal to the maximum expected blood loss for the type of procedure in a patient with normal haemostasis
Moderate	Intraoperative blood loss was higher than the maximum expected blood loss for the type of procedure performed in a patient with normal haemostasis, but haemostasis was controlled
None	Haemostasis was uncontrolled, necessitating a change in the clotting factor replacement regimen

7.2.5.2 At the End of the Postoperative Period (by Haematologist)

At the end of the postoperative period, the haemostatic efficacy of *Wilate* will be assessed by the haematologist using the criteria listed in **Table 4**.

Table 4 Efficacy Assessment at the End of the Postoperative Period

Excellent	No postoperative bleeding or oozing that was not due to complications of surgery. All postoperative bleeding (due to complications of surgery) was controlled with Wilate as anticipated for the type of procedure
Good	No postoperative bleeding or oozing that was not due to complications of surgery. Control of postoperative bleeding due to complications of surgery required increased dosing with Wilate or additional injections not originally anticipated for the type of procedure
Moderate	Some postoperative bleeding and oozing that was not due to complications of surgery. Control of postoperative bleeding required increased dosing with Wilate or additional injections not originally anticipated for the type of procedure
None	Extensive uncontrolled postoperative bleeding and oozing. Control of postoperative bleeding required use of an alternate VWF-containing product

7.2.5.3 *Overall Efficacy Assessment at the End of the Postoperative Period (by Investigator)*

Overall efficacy using the ‘excellent,’ ‘good,’ ‘moderate,’ and ‘none’ scale taking both the intra- and postoperative assessments into account will be assessed by the investigator based on the algorithm given in **Table 5**.

Table 5 Algorithm for the Overall Efficacy Assessment for Surgical Prophylaxis

Intraoperative assessment	Postoperative assessment			
	Excellent	Good	Moderate	None
Excellent	Excellent	Good	Good	Moderate
Good	Good	Good	Moderate	Moderate
Moderate	Good	Moderate	Moderate	None
None	Moderate	Moderate	None	None

7.2.6 Quality of Life

For the assessment of QoL, the following instruments will be used:

- Patient-Reported Outcomes Measurement Information System (PROMIS)-29 [5–7] for patients of all ages. For patients 6–7 years of age, the questionnaire will be completed by the parent/legal guardian. Self-reported measures will be used for patients ≥ 8 years old.
- 36-Item Short Form Health Survey, version 2 (SF-36v2, [8]), for patients ≥ 16 years,
- 10-Item Short Form Health Survey (SF-10, [9]) will be used for patients 6–15 years of age.

At each visit requiring QoL assessments, the questionnaires should be administered before starting any other visit assessment.

7.2.7 Joint Health Status

Joint health will be assessed using the Hemophilia Joint Health Score (HJHS) [10], which has been specifically validated for the assessment of clinical outcome in VWD [11].

Target joint(s) will also be documented. Target joint(s) are defined as having three or more spontaneous BEs into a single joint within 6 consecutive months preceding either the Baseline Visit or the Study Completion Visit.

7.2.8 Pictorial Blood Assessment Chart

Bleeding information from each menstrual period in this study will be collected in the Pictorial Blood Assessment Chart (PBAC) [12,13]. The PBAC will be provided to all female patients of child-bearing potential.

The investigator will train all relevant patients in how to complete the PBAC. At each study visit, the investigator will review the completed PBAC and calculate the PBAC score. In addition, the investigator will review, together with the patient, the severity assessment of the menstrual bleed using the criteria given in **Table 1, Section 7.2.2**. The data documented in the PBAC and the investigator-calculated final score will be recorded in the eCRF.

7.3 PK Assessments

PK parameters will be assessed for VWF:Ac (VWF:RCO) and FVIII:C using both the chromogenic (CHR) and one-stage (OS) assays based on actual IMP potencies.

The following PK parameters will be assessed:

- Area under the curve (AUC) and AUC normalized for the administered dose (AUC_{norm})
- In vivo half-life ($T_{1/2}$)
- Maximum plasma concentration (C_{max})
- Time to reach maximum plasma concentration (T_{max})
- Mean residence time (MRT)
- Volume of distribution (V_d)
- Clearance (CL)
- Incremental in vivo recovery (IVR)

7.4 Safety Assessments

7.4.1 Assessments for Safety Endpoints

The following drug safety information will be collected:

- Adverse events (AEs) and serious adverse events (SAEs) (for definitions and reporting requirements, see **Sections 7.4.2, 7.4.3, and 7.4.4**)
- Pregnancies, drug overdose, interaction, medication error, lack of efficacy, and post-study SAEs (see **Section 7.4.7**)

7.4.2 Adverse Events (AEs)

7.4.2.1 *Definitions*

- **Adverse event (AE):** An AE is any untoward medical occurrence in a study patient receiving an IMP and which does not necessarily have a causal relationship with this treatment. An AE can therefore be any unfavourable and unintended sign (including an abnormal laboratory finding), symptom, or disease temporally associated with the use of an IMP, whether or not related to the IMP.
- **Treatment-emergent adverse event (TEAE):** A TEAE is an AE that started or worsened after the start of IMP infusion.
- **Adverse drug reaction (ADR):** An ADR is any noxious and unintended response to an IMP related to any dose. The phrase ‘response to an IMP’ means that a causal relationship between the IMP and an AE carries at least a reasonable possibility, i.e., the relationship cannot be ruled out.
- **Other significant AEs:** Any marked laboratory abnormalities or any AEs that led to an intervention, including withdrawal of drug treatment, dose reduction, or significant additional concomitant therapy.
- **Withdrawal due to AE/ADR:** AE/ADR leading to discontinuation of treatment with IMP. Any such events will be followed up by the investigator until the event is resolved or until the medical condition of the patient is stable. All follow-up information collected will be made available to the Sponsor.

7.4.2.2 *Collection of AEs*

The condition of the patient will be monitored throughout the study. At each visit, whether scheduled or unscheduled, AEs will be elicited using a standard non-leading question such as “How have you been since the last visit/during the previous study period?” In addition, the investigator will check the patient diaries for any documented event.

Any AE or ADR which occurs during the study will be noted in detail on the appropriate pages of the eCRF. If the patient reports several signs or symptoms representing a single syndrome or diagnosis, the diagnosis should be recorded in the eCRF. The investigator will grade the severity of all AEs or ADRs (mild, moderate, or severe), the seriousness (non-serious or serious),

and the causality as defined in **Sections 7.4.2.3, 7.4.3, and 7.4.2.4**. The Sponsor is responsible for assessing the expectedness of each ADR (expected or unexpected) as defined in **Section 7.4.2.5**.

In the event of clinically significant abnormal laboratory findings, the tests will be confirmed and the patient followed up until the laboratory values have returned to normal and/or an adequate explanation for the abnormality has become available.

Diseases, signs and symptoms, and/or laboratory abnormalities already present before the first administration of IMP will not be considered AEs unless an exacerbation in intensity or frequency (worsening) occurs. Seroconversion for parvovirus B19 will be reported as an AE.

The investigator will provide detailed information about any abnormalities and about the nature of and reasons for any action taken as well as any other observations or comments that may be useful for the interpretation and understanding of an AE or ADR.

7.4.2.3 Severity of AEs

The severity of AEs will be graded as follows:

- **Mild:** an AE, usually transient, which causes discomfort but does not interfere with the patient's routine activities
- **Moderate:** an AE which is sufficiently discomforting to interfere with the patient's routine activities
- **Severe:** an AE which is incapacitating and prevents the pursuit of the patient's routine activities

The grading of an AE is up to the medical judgment of the investigator and will be decided on a case-by-case basis.

7.4.2.4 Causality of AEs

The relationship of AEs to the administered IMP will be assessed by the investigator:

- **Probable:** reports including good reasons and sufficient documentation to assume a causal relationship, in the sense of plausible, conceivable, likely, but not necessarily highly probable. A reaction that follows a reasonable temporal sequence from administration of the IMP; or that follows a known or expected response pattern to the suspected medicine; or that is confirmed by stopping or reducing the dosage of the medicine and that could not reasonably be explained by known characteristics of the patient's clinical state.
- **Possible:** reports containing sufficient information to accept the possibility of a causal relationship, in the sense of not impossible and not unlikely, although the connection is uncertain or doubtful, for example because of missing data or insufficient evidence. A reaction that follows a reasonable temporal sequence from administration of the IMP; that follows a known or expected response pattern to the suspected medicine; but that could readily have been produced by a number of other factors.

- **Unlikely:** reports not following a reasonable temporal sequence from IMP administration. An event which may have been produced by the patient's clinical state or by environmental factors or other therapies administered.
- **Not related (unrelated):** events for which sufficient information exists to conclude that the aetiology is unrelated to the IMP.
- **Unclassified:** reports which, for whatever reason, are not yet assessable, e.g., because of still outstanding information (can only be a temporary assessment).

7.4.2.5 Classification of ADRs by Expectedness

ADRs will be classified by the Sponsor as either expected or unexpected:

- **Expected:** an ADR that is listed in the current edition of the IB.
- **Unexpected:** an ADR that is not listed in the current edition of the IB or that differs because of greater severity or greater specificity.

7.4.2.6 Outcome of AEs

The outcome of all reported AEs has to be documented as follows:

1. Recovered, resolved
2. Recovering, resolving
3. Not recovered, not resolved
4. Recovered, resolved with sequelae
5. Fatal
6. Unknown

NOTE: A patient's **death** per se is not an event, but an outcome. The event which resulted in the patient's death must be fully documented and reported, even in case the death occurs within 4 weeks after IMP treatment end and regardless of whether or not it is considered treatment-related.

7.4.2.7 Action(s) Taken

AEs requiring action or therapy must be treated with recognised standards of medical care to protect the health and wellbeing of the patient. Appropriate resuscitation equipment and medicines must be available to ensure the best possible treatment in an emergency situation.

The actions taken by the investigator must be documented:

(a) General actions taken in the event of an AE

- None
- Medication (other than IMP) or other (e.g., physical) therapy started
- Test performed
- Other (to be specified)

(b) IMP-related actions taken in the event of an AE

- None
- Product withdrawn
- Dose reduced
- Dose increased

The investigator will follow up on each AE until it has resolved or until the medical condition of the patient has stabilised. Any relevant follow-up information will be reported to the Sponsor.

7.4.3 Serious Adverse Events (SAEs)

A **serious AE (SAE)** is any untoward medical occurrence that at any dose:

- results in death,
- is life-threatening (see below),
- requires hospitalisation or prolongation of existing hospitalisation,
- results in persistent or significant disability/incapacity,
- is a congenital anomaly/birth defect,
- is another important medical event (see below).

NOTE: The term '**life-threatening**' refers to an event in which the patient was, in the view of the reporting investigator, at immediate risk of death at the time of the event; it does not refer to an event which may hypothetically have caused death had it been more severe.

In deciding whether an AE/ADR is serious, medical judgment should be exercised. Thus, important AEs/ADRs that are not immediately life-threatening or do not result in death or hospitalisation but may jeopardise the patient or may require intervention to prevent one of the other outcomes listed in the definitions above should also be considered serious.

Examples of '**important medical events**' are all suspected transmissions of an infectious agent, which therefore have to be reported as SAE. A suspected virus transmission means that virus antigen has been detected in the patient. A passive transmission of antibodies alone does not constitute a suspected virus transmission. Another such '**important medical event**' that has to be reported as an SAE is the development of VWF or FVIII inhibitors.

7.4.4 AE and SAE Reporting Timelines

All SAEs, whether or not they are suspected to be related to study treatment, are to be reported immediately by telephone or email to the clinical study team.

Phone:	[REDACTED]
Mobile:	[REDACTED]
Email:	[REDACTED]

The contact details will also be communicated at the study initiation visit.

In addition, within 24 hours after recognition of an SAE, an Octapharma Serious Adverse Event Report must be completed and submitted to:

Octapharma's Corporate Drug Safety Unit
OCTAPHARMA Pharmazeutika Produktionsges.m.b.H.
[name]

Email:	[REDACTED]
24-hour emergency telephone number:	[REDACTED]

Waivers the from SAE Reporting Requirement

Waivers from the SAE reporting requirement include surgeries that are elective or were planned before study entry or prolongations of existing hospitalisations for economic or social, but not medical, reasons. Such surgeries or prolongations of hospitalisations should not be considered SAEs.

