6.1.13 Surgical Visits

Patients may undergo surgical interventions in the course of the study. Whether or not these patients will be hospitalised will depend on the type and severity of the surgery and be at the discretion of the investigator.

In patients undergoing major surgeries, standard methods of postsurgical thromboprophylaxis, such as gradated compression stockings and early mobilisation, should be used to prevent venous thromboembolism.

For the flow chart of assessments for surgical prophylaxis, see **page 27**.

For details on the surgery data to be documented and the surgical efficacy assessments to be performed, see **Section 7.2.4** and **Section 7.2.5**.

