9.2.3 Safety Analysis Plan

All safety analyses will be based on the SAF population.

The analysis of safety will be based on the occurrence of AEs, the results of the safety laboratory tests, and the occurrence of parvovirus B19 seroconversions.

AEs will be coded according to the latest Medical Dictionary for Regulatory Activities (MedDRA) version. The analysis will include only treatment-emergent adverse events (TEAEs), i.e., AEs that started or worsened after the first IMP infusion. All TEAEs, related TEAEs (i.e., TEAEs probably or possibly related to the IMP), and serious TEAEs will be summarised and tabulated according to MedDRA primary system organ class and preferred term.

Patient listings will be provided for patients with SAEs, AEs leading to withdrawal from study, and AEs leading to death.

Time profiles of the safety laboratory parameters will be analysed by presenting sampling statistics for the values as well as their difference to baseline at each time point. Additionally, frequency tables for values outside the normal ranges will be presented.

Similarly, time profiles of VWF and FVIII inhibitor testing results will be analysed by presenting sampling statistics for the values as well as frequency tables for positive findings, along with 95% Pearson-Clopper CIs.

To assess the viral safety of *Wilate*, incidences of parvovirus B19 seroconversions between baseline and end of study will be estimated along with 95% Pearson-Clopper CIs.

Other safety parameters (e.g., changes in physical examination findings) will be analysed by summary tables or listings.

The analysis of the safety parameters recorded during surgery (lab values) will be purely descriptive and presented as summary tables or listings.

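### The SAE waiver exempts any elective surgery, not only surgery planned before entry, and does not say that the underlying condition stays reportable

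*Protocol*

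**What the plan says.** Protocol section 7.4.4 lists what need not be reported as an SAE: "Waivers from the SAE reporting requirement include surgeries that are elective or were planned before study entry", together with longer hospital stays for economic or social reasons. It then makes this a rule of classification as well as of reporting: "Such surgeries or prolongations of hospitalisations should not be considered SAEs". The restriction to non-medical reasons belongs to the prolonged stays, not to the surgeries. 'Elective' is not defined.

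The general rules are in the preceding sections. Under 7.4.3 an untoward occurrence is serious if it "requires hospitalisation or prolongation of existing hospitalisation". Section 7.4.2.2 says that conditions present before the first dose "will not be considered AEs unless an exacerbation in intensity or frequency (worsening) occurs", so worsening on study is an AE. SAP section 4.9.1 counts as treatment-emergent any documented AE that began or worsened after the first infusion started.

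Surgery on study is foreseen. Section 6.1.13 says "Patients may undergo surgical interventions in the course of the study", and both documents define a surgery analysis set. For output, protocol section 9.2.3 says that all TEAEs, related TEAEs "and serious TEAEs will be summarised and tabulated according to MedDRA primary system organ class and preferred term", with patient listings of SAEs. SAP section 4.9.1 plans the corresponding table and listing.

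**The concern.** A waiver for surgery planned before entry is sound, because the reason for the operation predates the study product. That reasoning does not extend to an operation first arranged during the 12 months of treatment for something that arose or got worse in that time. By waiving elective surgery without limit of timing or cause, 7.4.4 lets the way an operation was arranged bear on whether the admission is treated as serious. The definitions in 7.4.2.2 and 7.4.3 give no weight to that.

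At stake are the serious TEAE table, the SAE listing and the 24-hour report to the sponsor's drug safety unit. The trial has one arm, so there is no concurrent group in which the same reporting practice would operate and offset the effect. With about 14 sites (protocol section 3.2) and no definition of 'elective', like cases may also be handled differently from one site to another.

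**Working it through.** There is no figure in the plan to reproduce: neither document states an expected number or rate of SAEs or of surgeries. The check is mainly a reading of the text.

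**Step 1: scope of the waiver.** The grounds in 7.4.4 are alternatives. If 'elective' meant only surgery already planned at entry, the second ground would add nothing. The plain reading is that elective surgery arranged on study is waived.

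**Step 2: the rules side by side, for a patient admitted for elective surgery arranged on study because of a new or worsened condition.**

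| Provision | Result |
|---|---|
| Protocol 7.4.2.2 | the new or worsened condition is an AE |
| SAP 4.9.1 | it is treatment-emergent |
| Protocol 7.4.3 | it is serious if it requires hospitalisation |
| Protocol 7.4.4 | the surgery is not an SAE; nothing is said about the condition |

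The gap is in the last row. A site can report the condition as serious under 7.4.3, or treat the whole admission as waived under 7.4.4. The text does not settle which.

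**Step 3: can the event be recovered later?** The surgery record in protocol section 7.2.4 captures whether an operation was planned or an emergency, its location, its severity and a short narrative. It lists no item that links the operation to a new or worsened condition. The SAP surgery set (section 3.5) holds only patients given study product before the operation, so it need not contain every surgery. SAP section 4.9.1 has no step that reconciles surgeries with SAEs.

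**Step 4: arithmetic per patient.** Inputs: N = 40 (protocol section 3.2) and N = 28 (SAP section 1.5). The number of affected patients is an assumption. Incidence counts patients, so a patient changes it only if he or she has no other serious TEAE. The change per such patient is 100/N:

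- N = 40: 100/40 = 2.5 percentage points
- N = 28: 100/28 = 3.6 percentage points

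As an illustration, suppose exactly one patient is affected and nobody else has a serious TEAE. The exact (Clopper-Pearson) 95% upper limit is 1 − 0.025^(1/N) for 0 of N. For 1 of N it is the p that solves (1 − p)^N + N·p·(1 − p)^(N−1) = 0.025.

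| N | Patient left out: 0 of N | Patient counted: 1 of N |
|---|---|---|
| 40 | 0.0%, upper limit 8.81% | 2.5%, upper limit 13.16% |
| 28 | 0.0%, upper limit 12.34% | 3.6%, upper limit 18.35% |

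**The case against.** The best answer is that the waiver names the procedure and not the disease. It does not amend 7.4.3, which adds: "In deciding whether an AE/ADR is serious, medical judgment should be exercised". Section 7.4.2.6 draws a similar line for death, which it treats as an outcome whose causing event must be reported. On this reading the operation is waived, the condition remains assessable as an SAE, and only a clarifying sentence is missing. This largely stands. A reader might infer that the waiver overrides the seriousness criteria, or that such events would be missing. The documents do not support either inference, because a careful investigator can still report the condition. But nothing requires it, and the wording as it stands is wider than its rationale.

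Second, 'elective' is not the same as scheduled, and an operation made necessary by a new bleeding source might not be called elective. That is fair, and it is a further reason to define the term.

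Third, other records limit the loss. The condition should still be an AE and appear among all TEAEs. Gastrointestinal bleeds are recorded as major bleeding episodes (7.2.2), continued bleeding despite treatment is reportable as lack of efficacy (7.4.7), AEs are monitored around surgery (7.2.4), and stays prolonged for medical reasons fall outside the waiver. Patients with cervical or uterine causes of abnormal bleeding are excluded at entry (4.1.3), although such a cause could arise later. All this stands: what is at risk is the seriousness classification and the outputs that depend on it. It also rules out calling the serious TEAE count the trial's main safety figure, since neither document ranks it above the other safety outputs.

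**Conclusion.** The concern holds as a matter of wording. Section 7.4.4 exempts any elective surgery and is silent on the underlying condition, so an admission for elective surgery arranged on study for a new or worsened condition can be omitted from the serious TEAE table, the SAE listing and expedited reporting. This rests on the plain reading of 'or' and on the absence of any other provision that keeps the condition reportable as serious. Events that are serious on another criterion, such as death, threat to life, disability or inhibitor development, are not removed.

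The frequency cannot be estimated from the documents. Only the effect per patient can be stated: 2.5 points (N = 40) or 3.6 points (N = 28) for each affected patient with no other serious TEAE. A reader might go on to infer a particular understatement of the SAE rate. That would need assumed counts both of waived patients and of other patients with SAEs, and the documents supply neither.

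**What to change.** In protocol section 7.4.4, limit the surgical waiver to operations planned before study entry for a condition that has not worsened since the first dose of study product. Add that for any other surgery the underlying condition is recorded as the AE and assessed for seriousness under 7.4.3, and that complications of any surgery remain reportable.

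If the protocol can no longer be amended, reconcile every on-study surgery record with the AE and SAE entries before database lock. The SAP's data review meeting is a natural place for this. Use all surgery records and not only the surgery analysis set.

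The cost is a short wording amendment, which under section 10.4 needs agreement with the co-ordinating investigator and submission as regulations require. A few more SAE reports and a slightly less favourable serious TEAE count may follow. The change concerns reporting only.
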